8.3.7. Prior and Concomitant Medications

Prior and concomitant medications will be coded using the World Health Organization (WHO) drug dictionary. Prior and concomitant medications will be summarized by treatment group, ATC2 class, and preferred term. A subject who takes one or more medications under any given ATC2 class and preferred term will be counted once for the ATC2 class and preferred term.

For the summary, medications taken prior to the first dose of study medication will be classified as prior medications, while medications taken on or after the first dosing will be classified as concomitant medications. Medications taken prior to the first dosing but with a missing stop date or with a stop date either on or after the first dosing or marked as "continuing" will also be considered concomitant medications for the summary. A listing of prior and concomitant medications by subject will be provided for the Safety Analysis Set.

8.3.8. Physical Examinations

A listing of physical examination data by subject for the Safety Analysis Set will be provided.

8.3.9. Analysis of Other Safety Variables

HAHA results (positive as determined by titer values, if positive on screening, and detection of neutralizing antibody, if needed) will be listed to identify subjects with positive HAHA.

ECOG performance status at baseline and scheduled time of evaluation (including end of Treatment visit) will be summarized by treatment group and in total for Safety Analysis Set. A two-way frequency tabulation for baseline and each study visit will be provided for ECOG performance status.

Left ventricular ejection fraction (LVEF) will be summarized using descriptive statistics for actual values and for changes from baseline by cohort by scheduled time of evaluation including the end of treatment visit as well as for the minimum and maximum post-baseline values and for the last observation on treatment. The last observation on

treatment value is defined as the last non-missing value on or prior to end of treatment duration plus 7 days. Repeated or unscheduled tests will not be summarized for each scheduled visit, but will be included for summaries of maximum and minimum post-baseline values and the last observation on treatment.

A listing of ECOG performance status will be presented.

A listing of echocardiogram by subject for the Safety Analysis Set will be provided.

8.4. Pharmacokinetic Analyses

8.4.1. Concentration Data

Concentrations below the lower limit of quantitation (BLQ) will be set to zero for the calculation of descriptive statistics. If any of the concentrations at a time point is BLQ, the geometric mean of the concentrations at this particular time point will not be calculated and will be presented as “NC” in the summary tables. PK data will be listed for the pharmacokinetic analysis sets.

8.4.1.1. Sparse Patritumab PK

Serum concentrations for patritumab at Cycles 1-3 and at End of Study Treatment will be listed and summarized with descriptive statistics using the PK Analysis set. Mean plasma concentration of patritumab versus time will be plotted on both linear scale and semi-logarithm scale.

8.4.1.2. Intensive PK

Intensive PK refers to samples taken during Cycle 1 (Day 1 to Day 21 for patritumab, Day 1 to Day 8 for cetuximab, Day 1 to Day 3 for cisplatin or carboplatin). Individual concentration profiles versus time by treatment group for each study drug will be plotted on linear and logarithmic scales. Concentrations will be summarized by treatment and nominal timepoint. Individual PK parameters will be listed and summarized by treatment.

The PK parameters, area under curve at last time point (AUC_{last}) and C_{max} will be summarized and listed by treatment group for each drug using the PK Analysis set. Box plots of AUC_{last} and C_{max} versus treatment will be presented.

8.4.2. Analysis of Pharmacokinetic (PK) Parameters

The intensive PK parameters, area under curve at last time point (AUC_{last}) and C_{max} will be summarized and compared for cetuximab and platinum concentration by treatment arms for the PK Analysis set. The possible drug-drug interactions between patritumab plus cetuximab or cisplatin/carboplatin, the PK of serum cetuximab and platinum concentrations will be compared with and without patritumab using an ANOVA model with treatment as factor. AUC_{last} and C_{max} will be log-transformed prior to analysis. The geometric mean ratios and their two-sided 90% CIs for AUC_{last} and C_{max} between the patritumab arm and the placebo arm will be calculated using the exponentiation of the differences and their CIs between treatments least square mean from the ANOVA. The ratios and their two-sided 90% CIs will be expressed relative to the placebo arm.

8.4.3. Population Pharmacokinetic (PK) and Exposure Response

For all subjects, sparse samples for serum patritumab concentrations will be assessed using population PK methods. The relationship between exposure and response will be explored using population PK modeling. These analyses are outside the scope of this SAP and details of those analyses will be included in a separate document for population PK and exposure response analyses.

8.5. Pharmacodynamic (PD) Parameters

Not Applicable.

8.6. Biomarkers Analyses

The study has baseline HRG biomarker and HPV status assessments to determine the stratification factors of HRG and HPV. Baseline HRG cutoff will be used for all specified efficacy analyses. As exploratory analyses, the HRG cutoff will be refined using graphic technique, data distribution, maximum likelihood methods, and clinical benefit of HRG high group. Selected efficacy analyses for the HRG high stratum will be performed using the refined HRG cutoff as additional exploratory analyses. Further biomarker evaluations will be summarized descriptively.

Baseline HRG values will be summarized and listed.

8.7. Other Variables Analyses

8.7.1. Patient Reported Outcomes

The FACT-H&N total score (FACT-G +disease specific subscale score), the FACT-H&N individual subscale scores (Physical Well Being (PWB), Social Well Being (SWB), Emotional Well Being (EWB), Functional Well Being (FWB)), FACT-G total score, and the FACT-H&N FHNSI score and change from baseline will be summarized by visit and treatment group using the FACT-H&N Analysis Set.

For each post-baseline assessment:

- Observed range; Mean (SD) by treatment group (overall, HPV+ and HPV-) will be reported for each of the scores listed above.
- The entire Cumulative Distribution Function (CDF) of change from baseline on FACT-G, FACT-H&N FHNSI and FACT-H&N total score will be presented as a continuous plot of the change from baseline on the X-axis and the cumulative percent of subjects experiencing that change on the Y-axis for each treatment group.

Change from baseline in the FACT-H&N total score (FACT-G +disease specific subscale score), the FACT-H&N individual subscale scores, FACT-G total score, and the FACT-H&N FHNSI score, will also be evaluated using mixed longitudinal modeling for the FACT-H&N Analysis Set. The model will include treatment, time, treatment-by-time interaction, and baseline as fixed effects. The unstructured option for the REPEATED statement in PROC MIXED will be used to model the within subject covariance

structure. LS means along with 95% CIs by timepoint and LS mean differences between the control arm and patritumab arm along with two-sided 95% CIs for each timepoint will be derived.

For these analyses, PRO values obtained at the end of treatment visit or at any scheduled timepoint with fewer than 5 subjects in the placebo arm or patritumab arm will not be included.

Descriptive statistics for the actual value and change from baseline will be computed for the EQ-5D-5L health profile utilities and EQ-5D VAS by scheduled time of evaluation (including end of treatment visit) for all subjects and by treatment group using the EQ-5D Analysis Set. Results of the EQ VAS will be presented as a measure of overall self-rated health status.

Approved

9. CHANGES FROM THE PROTOCOL SPECIFIED STATISTICAL ANALYSES

No changes have been issued.

Approved

11. APPENDICES

11.1. Data Derivation Details

11.1.1. Windows Convention for Handling Partial and Missing Dates

No imputation will be performed for any dates other than adverse event onset dates and concomitant medication start and stop dates. A complete date may be necessary in order to determine if an adverse event or medication should be included in the summary/analysis (i.e., if the event is treatment emergent or the medication is prior or concomitant). The conventions specified below will be used for this purpose only. The original partial or missing dates rather than the imputed dates will be presented in the listing.

Adverse Events Onset Date

If the AE onset date is missing in which the day, month, and year are all unknown or only the day is known, the AE onset date is set to the date of first dose of study medication.

For the partial AE onset date,

- If the year is present and the month and day are missing or the year and day are present and the month is missing
 - If year = year of first dose then set month and day to month and day of first dose
 - If year < year of first dose, then set month and day to December 31st.
 - If year > year of first dose, then set month and day to January 1st.
- If the month and year are present and the day is missing:
 - If year = year of first dose and
 - if month = month of first dose then set day to day of first dose date
 - if month < month of first dose then set day to last day of month
 - if month > month of first dose then set day to 1st day of month
 - If year < year of first dose then set day to last day of month
 - If year > year of first dose then set day to 1st day of month
- If the imputed AE onset date is after AE stop date, then set the onset date to the AE stop date.

Prior and Concomitant Medications Date

If the start date of medication is completely missing in which the day, month, and year are all unknown or only the day is known, then the start date will not be imputed.

For the partial start date of medication,

- If the year is present and the month and day are missing or the year and day are present and the month is missing, set month and day to January 1.
- If the year and month are present and the day is missing, set day to 1st day of month.
- If the imputed start date of medication is after the non-imputed end date of medication, then the start date will be set to the end date of medication.

If the end date of medication is completely missing which the day, month, and year are all unknown or only the day is known, then the end date will not be imputed.

For the partial end date of medication,

- If the year is present and the month and day are missing or the year and day are present and the month is missing, set month and day to December 31.
- If the year and month are present and the day is missing, set day to last day of the month.

Incomplete Tumor Assessment Dates

All dates for tumor assessment must be completed with day, month and year.

- If one or more measurement dates (e.g. X-ray, CT-scan for target and non-target tumor lesions) are incomplete but other measurement dates are available, this/these incomplete date(s) are not considered for calculation of the assessment date.
- If all measurement dates have no day recorded, the 1st of the month is used.
- If the month is not completed, for any of the assessments, the respective assessment will be considered to be at the midpoint of previous and following assessment dates.

Incomplete Dates for Last Contact or Death

All dates are expected to be completed with day, month, and year.

If the day/month is missing, the 1st of the month/year will be used for incomplete death dates or dates of last contact.

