5.1.2.1. Overall Survival (OS)

OS is defined as the time from the date of randomization to death due to any cause. Subjects who are alive at the time of data cut off for OS analysis will be censored at the last contact date at which the subject is known to be alive.

Survival status data will be obtained from deaths reported in the CRFs and Survival follow-up communications every 3 months after a subject discontinues from study treatment.

The last contact date is defined as the last date the subject was known to be alive at the analysis cut-off. The date will be the latest date among the following:

- Last non-missing assessment/onset date captured under the following eCRF pages (or if a date of assessment/onset is not available the “date of visit” for the eCRF page can be used): adverse events, vital signs, physical examination, ECOG PS, ECG, Echocardiogram or MUGA scan, safety laboratory test, tumor assessment, patient-reported outcomes assessment, hospitalization and also assessment date in third-party data such as PK, HAHA etc.
- Last dosing date of study medication, last date of concomitant medications, and last date of non-drug treatments/procedures.
- Start date of subsequent anti-cancer therapy administered after study treatment discontinuation.
- Date of Last Contact collected on the survival follow up page of the eCRF.

- Date of Last Contact collected on the final subject status (or end of study status) page of the eCRF.

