7.2. Handling of Dropouts or Missing Data

For a description of the handling of censored data for efficacy endpoints such as OS, PFS and TTP, see Section 5.1 above. Imputation of partial or missing AE onset date and concomitant medication date, incomplete tumor assessment dates, and incomplete dates for last contact or death are specified in Section 11.1. The missing data handling for the analyses on patient reported outcomes is described in 5.6.2.1.

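### Incomplete death dates are set to the 1st of the month or year with no floor, so an imputed death can precede the last date known alive or randomisation

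*SAP*

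**What the plan says.** The last part of SAP 11.1.1 deals with incomplete dates of last contact or death. It states an expectation, "All dates are expected to be completed with day, month, and year", and then the rule for a missing day or month: "the 1st of the month/year will be used for incomplete death dates or dates of last contact". No lower limit follows. SAP 7.2 adds no rule of its own and only points back: "incomplete dates for last contact or death are specified in Section 11.1".

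The clock starts at randomisation: "OS is defined as the time from the date of randomization to death due to any cause". SAP 5.1.2.1 also defines a last date known alive from many eCRF and third-party sources: "The last contact date is defined as the last date the subject was known to be alive at the analysis cut-off". Its only stated use is censoring: "Subjects who are alive at the time of data cut off for OS analysis will be censored at the last contact date". It is not linked to an imputed death date.

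SAP 11.1.1 opens with a sentence that conflicts with the death rule: "No imputation will be performed for any dates other than adverse event onset dates and concomitant medication start and stop dates". It restricts the conventions to deciding whether an event is treatment-emergent or a medication prior or concomitant, and then gives rules for tumour assessment, last-contact and death dates as well.

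**The concern.** The rule picks the earliest day compatible with the recorded month or year and does not check it against anything else known about the subject. Someone seen in clinic on the 22nd whose death is recorded only by month is dated as dead on the 1st. If randomisation fell in that same month or year, survival time can be negative, and the SAP does not say what to do with a negative time.

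The same section does protect less important dates. An imputed adverse event onset may not pass the event's stop date, and an imputed medication start may not pass its end date. A death date, which defines an efficacy event, has no such check.

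The opening sentence is a second problem. Read literally, it means that death dates are not imputed at all, so two programmers could build different OS datasets from one section.

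**Working it through.** There is no planned figure to reproduce, so the check applies the rule to calendar dates.

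**Inputs.** The rule is from SAP 11.1.1 and the time origin from SAP 5.1.1 and 5.1.2.1. Survival contact is about every 3 months (SAP 5.1.2.1; Protocol 6.3), taken as 91 days. Assumptions: true death dates spread evenly over 2016 and 2017 (731 days); the gap between last contact and death; and, for the third step, median OS, which the documents do not give.

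**1. Size of the shift.** In a period of m days the shift runs from 0 to m − 1, so the shifts sum to m(m − 1)/2.
- Day missing: fourteen 31-day months, eight 30-day months and Februaries of 29 and 28 days give (14 × 465 + 8 × 435 + 406 + 378)/731 = 10,774/731 = 14.7 days on average; maximum 30.
- Month missing: (366 × 365/2 + 365 × 364/2)/731 = 133,225/731 = 182 days on average, or 182/30.4 = 6.0 months; maximum 365 in a leap year.

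**2. How often an imputed death precedes the last contact.** This is the share of days whose shift exceeds the gap from last contact to death.

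| Gap (days) | Day missing | Month missing |
|---|---|---|
| 7 | 73.7% | 97.8% |
| 14 | 50.8% | 95.9% |
| 21 | 27.8% | 94.0% |
| 30 | 0% | 91.5% |
| 91 | 0% | 74.8% |
| Even over 0–91 | about 16% | about 87% |

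**3. How often it precedes randomisation.** A year-only death in the calendar year of randomisation goes to 1 January of that year, which is before randomisation unless the subject was randomised on that day. For a wider view, assume exponential survival, randomisation spread over one calendar year and a median OS of 6 to 14 months. Simulation then gives 5.6% (median 6) to 2.4% (median 14) of day-missing deaths, and 46% to 25% of month-missing deaths.

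All percentages in steps 2 and 3 are conditional on the date being incomplete.

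**4. Illustrative subjects.** OS in days from randomisation. The floor column takes the later of the imputed date and the last contact; it is the same whether day or month is missing.

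| Randomised | Last contact | Died | True OS | Day missing | Month missing | With floor |
|---|---|---|---|---|---|---|
| 10 Aug 2016 | 22 Aug 2016 | 27 Aug 2016 | 17 | −9 | −222 | 12 |
| 15 Mar 2016 | 20 Oct 2016 | 28 Oct 2016 | 227 | 200 | −74 | 219 |
| 10 Aug 2016 | 18 May 2017 | 25 May 2017 | 288 | 264 | 144 | 281 |

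With the floor, the remaining error is the gap from last contact to death: 5, 8 and 7 days here.

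**5. PFS.** SAP 5.1.1 censors a death more than 13 weeks (91 days) after the last evaluable scan. A death 100 days after that scan, on the 21st of a month with the day missing, moves 20 days early to day 80 and changes from censored to event.

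**The case against.** The strongest reply is that the rule will seldom be used. The SAP expects complete dates. Death is a serious adverse event reported within 24 hours of awareness, with a narrative (Protocol 9.4.2, 9.5), and data are reviewed for omissions and discrepancies (Protocol 12.3). Death certificates are a named source after consent is withdrawn (Protocol 4.1.6). A year-only date is hard to reconcile with contact about every 3 months. A negative time needs death in the same recorded month or year as randomisation, and for the month case that is an early death, when reporting is closest. All of this stands and limits the weight of the point. None of it supplies a bound for the dates that do arrive incomplete.

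Four stronger readings are tempting, and the documents do not support them.
- A reader might infer that negative times would be dropped silently, removing events from the full analysis set. Neither document says how such times are handled. Listing 16.2.6.2 shows randomisation, last contact, death and survival days side by side, so they would be visible. Even one lost event matters little: with power = Φ(√d/2 × |ln 0.56| − 1.2816), 53 events give 79.6% and 52 give 79.1%.
- A reader might set the 6-month shift against the assumed PFS medians of 4.2 and 7.5 months and see the primary result at risk. That shift needs a year-only death date, and PFS is affected only where the death date matters.
- A reader might infer bias between arms. The rule is identical in both, and no directional effect is shown.
- A reader might take the opening sentence to mean that deaths are not imputed. SAP 7.2 makes the intent to impute clear, so that sentence is an error of wording.

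**Conclusion.** The point holds as a defect in a stated rule. SAP 11.1.1 can place a death before a date on which the subject was documented alive, or before randomisation, and nothing in the protocol or SAP prevents it. When the rule is used, the error averages about 15 days for a missing day and about 6 months for a missing month, given evenly spread true dates. How often it will be used is unknown and probably low. OS is the endpoint most exposed; PFS is touched only where the death date supplies or reclassifies the event. The contradiction within 11.1.1 is real and needs correcting however many dates are incomplete. This is worth settling before unblinding because it costs almost nothing, and not because the primary conclusion depends on it.

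**What to change.** In SAP 11.1.1, for both missing-day and missing-month cases, set the death date to the latest of:

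1. the date imputed under the present rule;
2. the last date known alive under SAP 5.1.2.1, using complete, non-imputed dates only;
3. the randomisation date.

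Query any case in which the last date known alive is later than the recorded month or year of death; otherwise the result stays within the recorded period.

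Do not add a day to the last date known alive. Last alive on 31 March with death recorded as March would become 1 April. Nor should a missing month be replaced by last contact plus one day: last alive on 18 November 2016 with death recorded as 2017 would become 19 November 2016, in the wrong year, whereas the latest-of rule gives 1 January 2017.

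The floor does not remove all early dating, since the result is still the earliest date consistent with the record. It removes the impossible dates.

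Amend the opening of 11.1.1 to include tumour assessment, death and last-contact dates among those imputed, in line with SAP 7.2, and widen its statement of purpose to match.

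The cost is two or three sentences in the SAP and one line in the derivation, with no new data.

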11.2. Interim Analysis Statistical Analysis Plan

Safety data and efficacy data will be prepared for the purpose of DMC reviews, and the frequency and extent of such data reviews will follow the DMC charter for Study U31287-A-U203. In general, the statistical methodology and TLF shells in the SAP will be a framework to generate outputs for DMC reviews. The independent Data Analysis Group (DAG) will perform the analysis. Operating details of the DAG are included in the DMC charter.

Approved

11.3. Formula for Wilson MethodWilson Method

Use the following formula to compute a (1- α)% confidence interval for a single proportion using the Wilson method with continuity correction:

$$L = \frac{\hat{p}_i + \frac{z^2}{2n_i} - \frac{1}{2n_i} - z \sqrt{\frac{\hat{p}_i[n_i(1 - \hat{p}_i) + 1]}{n_i^2} + \frac{z^2 - 2 - 1/n_i}{4n_i^2}}}{1 + \frac{z^2}{n_i}}$$

$$U = \frac{\hat{p}_i + \frac{z^2}{2n_i} + \frac{1}{2n_i} + z \sqrt{\frac{\hat{p}_i[n_i(1 - \hat{p}_i) - 1]}{n_i^2} + \frac{z^2 + 2 - 1/n_i}{4n_i^2}}}{1 + \frac{z^2}{n_i}}$$

where \hat{p}_i denotes the sample proportion for group i and n the group sample size. All statistical constants will be computed using appropriate SAS functions. Note: if $\hat{p}_i=0$, L must be taken as 0; if $\hat{p}_i=1$, U is then 1. In case L is calculated to be less than 0, set L to 0; and similarly set U to 1 if U is calculated to be larger than 1.

Confidence limits for the difference in ORR between each of the U3-1287 (AMG888) groups and placebo based on Wilson (Newcombe) score will use the method below.

Denote the lower and upper Wilson score (with continuity correction) confidence limits for p_1 as L_1 and U_1 and the lower and upper confidence limits for p_2 as L_2 and U_2 (where L and U are defined above). The Wilson score (with continuity correction) confidence limits for the proportion difference ($d=p_1-p_2$) are computed as

$$d_L = (\hat{p}_1 - \hat{p}_2) - z \sqrt{L_1(1-L_1)/n_1 + U_2(1-U_2)/n_2}$$

$$d_U = (\hat{p}_1 - \hat{p}_2) + z \sqrt{U_1(1-U_1)/n_1 + L_2(1-L_2)/n_2}$$

